3.11 Analytical methods

Qualitative data from diary entries and exit interviews will be coded and analyzed using inductive content analysis to extract themes. Usability data from the SUS will be reported using descriptive statistics and compared against the benchmark score of 68, which represents average usability.

3.12 Objective

The Acify! App will be developed that can be easily navigated and understood by the user.

4.0 OVERVIEW OF CLINICAL TRIAL

4.1 Study Objectives

- 4.1.1 **Primary Objectives:** Assess and compare treatment acceptability across treatment arms.
- 4.1.2 **Secondary Objectives:** Preliminarily assess efficacy and mechanism of change for the behavioral activation app (Actify) vs. the USCPG app (QuitGuide) for smoking cessation.
- 4.1.3 **Tertiary Objectives:** Determine whether there is evidence of differential efficacy in smokers with vs. without pre-quit depressive symptoms

4.2 Study Population:

We will recruit 240 adult smokers, both with (PHQ=8 score 5-19; n=120) and without (PHQ-8 score 0-4; n=120) depressive symptoms, who are interested in quitting smoking. Participants will be recruited nationally via recruitment strategies used successfully in our previous studies: targeted Facebook ads, Craigslist ads in states with a high prevalence of smoking or racial/ethnic minority residence (to achieve the target 25% racial/ethnic minority representation in the sample), other free methods of advertising on the Internet (e.g., Reddit, Twitter), ResearchMatch.org, and earned media generated by press releases from the Fred Hutch media team.

Inclusion of Women & Minorities.

Our previous trials suggest that, without intervention to diversify the sample, the vast majority of participants would be Caucasian and female. To attain adequate representation of racial/ethnic minorities and men, we will cap enrollment of Caucasians and women at 75% of the sample via our online screening and enrollment process for the pilot trial. We anticipate that these caps will be necessary and that the resulting sample will be 25% male and 25% racial/ethnic minority. If needed, we will use targeted Facebook and Twitter campaigns specifically to recruit men and/or people with racial/ethnic minority affiliations (the ad platform's proxy for race/ethnicity). Based on demographic data from our recent trial of a technology-delivered cessation intervention using similar recruitment procedures [8], we expect the following percentages of racial minority participants: African American (10%), Native American or Alaska Native (2%), Native Hawaiian or Pacific Islander, Asian (2%), or other/multiple races (5%). In terms of ethnicity, we expect 8% to identify as Hispanic or Latino.

4.3 Study Design

This is a pilot, randomized controlled trial (n=240) to test the primary outcome of treatment acceptability and secondary outcomes of efficacy and mechanism of change for the Actify app vs. the active control app (the National Cancer Institute's QuitGuide app). We will test the interventions using an 8-week treatment period, and, consistent with the evaluation period in our previous cessation app pilot study, our primary outcomes will be assessed at the 8-week end-of-treatment mark. We will also collect 6-month follow-up data to assess long-term outcomes.

- 4.3.1 **Primary Endpoints:** Treatment acceptability as indicated by user satisfaction with assigned treatment (user satisfaction ratings of the assigned app at 8 weeks post-

randomization) and app utilization (total number of app server-recorded openings of the assigned intervention)

4.3.2 Secondary Endpoints: Treatment efficacy (smoking cessation) and changes to theory-based mechanisms of change (behavioral activation).

- Treatment efficacy:
 - Self-reported 30-day point prevalence abstinence (PPA) from smoking at 8 weeks post-randomization
 - Self-reported 30-day PPA from smoking at 6 months post-randomization; Biochemically-confirmed 30-day PPA from smoking at 8 weeks and 6 months post-randomization; Self-reported and biochemically confirmed 7-day PPA from smoking at 8 weeks and 6 months post-randomization; Self-reported and biochemically confirmed 30-day PPA from cigarettes and other non-medicinal nicotine/tobacco products at 8 weeks and 6 months, including e-cigarettes
- Mechanisms of change:
 - Change in behavioral activation from baseline to 8 weeks post-randomization
 - Change in depressive symptoms from baseline to 8 weeks post-randomization

4.3.3 Exploratory Endpoints: Differences in treatment effects by pre-quit depression (depressed vs. not depressed)

4.4 Estimated Accrual:

We estimate that our recruitment efforts will yield 904 screened, 490 eligible, 416 consented, and 240 randomized into the trial (120 per arm). We conservatively allotted 9 months for recruitment (26 enrolled/month).

4.5 Name of Sponsor/Funding Source:

National Institute on Drug Abuse, Grant Number: 1R34DA050967

5.0 SUBJECT ELIGIBILITY

5.1 Inclusion Criteria

- age 18 or older
- current smoker, averaging at least 5 cigarettes/day for the last 30 days
- interested in quitting smoking in the next 30 days
- experience downloading and using one or more apps on their smartphone
- either screens negative (PHQ-8 score 0-4) for depression (n=120) or screens positive for mild to moderate current depressive symptoms (PHQ-8 score 5-19; n=120)
- willing and able to complete all study activities including willing to receive study compensation by mail
- comfortable reading and writing in English
- have a mobile data plan and/or access to WiFi to support the use of the Actify app
- reside in the US

- have a smartphone either an iPhone (running iOS version 11 or higher) or an Android phone (running version 5.0 or higher)

5.2 Exclusion Criteria

- currently receiving behavioral treatment for depression (e.g., psychotherapy)
- current use of a depression app
- severe depression (PHQ-8 \geq 20)
- receiving other treatment for smoking cessation
- previous use of the QuitGuide program
- current or recent (within the past year) enrollment in a Fred Hutch smoking cessation study
- employees/family of investigator or study center
- member of the same household as another participant
- woman who is pregnant or breastfeeding, or planning to become pregnant
- currently incarcerated
- Is ineligible per fraud prevention protocol

6.0 SUBJECT REGISTRATION

Recruitment materials will direct potential participants to a recruitment website, which provides basic information about the study and a portal to the informed consent form, screening, and baseline surveys.

For participants who screen eligible on the recruitment website and provide their email address, we will instantly send them an email (and two reminders over a 14-day period) inviting them to complete a secured online survey to provide informed consent and complete the baseline assessment. Those not consenting and completing the online enrollment process within 14 days will be sent an email notifying them that they were not enrolled and providing both the QuitGuide app and the 1-800-QUIT-NOW phone number to reach their state's quitline. Both arms will be described as smartphone apps designed to assist with quitting and containing tools to improve mood.

[figure not shown]
To address potential fraudulent responses to web-based screening surveys with compensation for participation, we will use the same methods used in our previous studies: CAPTCHA verification, ineligibility if the IP address was previously used or suspicious, and telephone contact by research staff if any aspect of automated data collection revealed suspicious activity (e.g., very brief survey completion times or unusual patterns in email addresses). To further deter fraudulent attempts to enter the study, no compensation will be provided for completion of the screening and baseline surveys.

Participants completing this process will be enrolled in the study. This information will be stored in a secure research database behind FHCRC firewall. See section 7.2 Enrollment Procedures for more details.

7.0 TREATMENT PLAN

7.1 Treatment Plan Overview

Figure 2. Study Flow Chart

7.2 Description of the interventions

QuitGuide app. QuitGuide was created by the NCI's Smokefree team. It contains brief quit advice; a tool for tracking smokefree days and a statistics menu for viewing progress; a tool for tracking cravings and receiving a brief, related tip in response; a "Learn to Quit" feature with information on steps to prepare, cravings, withdrawal, slips, and staying smokefree. QuitGuide also has a "Manage My Mood" feature on the main page that gives it credibility as an intervention for smokers with depression, but with minimal expected efficacy due to the limited nature of the feature—i.e., recording a mood state and having the option to journal, call a friend, view photos and notes, or view a tip or distraction for handling difficult mood states. An example tip offered for handling negative affective states: "Distract. Do a crossword puzzle, play a game, or start a book that's been gathering dust."

Actify. Consistent with the BAT-D treatment model, the core functions of the current version of Actify are: (1) introducing the user to the program by describing the rationale for behavioral activation as an intervention for both depressive symptoms and smoking cessation, (2) helping the user to identify personal values, important life areas and meaningful activities associated with their values that will replace smoking habits (e.g., reading to my children), (3) prompting the user to schedule meaningful activities and providing reminders to complete them and, (4) visualizing overall progress toward meeting activity goals as well as the relationship between activities completed and mood. The app also contains tailored messages for smoking status and activity completion and resource sections with guidance for starting and maintaining a smoke free life. To increase engagement, the user receives daily tips, personalized feedback on money saved by cutting down/quitting smoking, feedback on activities completed, inspirational messages, user stories and quotes of ex-smokers overcoming challenges, noticing the benefits of quitting and how behavioral activation helped them to improve their mood and quit smoking. User stories illustrating how values can be translated into actions were associated with cessation in our prior work [69]. To acknowledge and motivate continued progress, the user is able to earn badges for smoke free streaks, usage of the app, and activity completion.

In-app notifications will be used to provide reminders to use the program, to track daily smoking and activity completion, and to remind users of upcoming scheduled activities. We added a Quit Guide section to the app, similar to QuitGuide's "Learn to Quit" menu, that it is available for reference if users need on-demand assistance. Portions of the QuitGuide are also presented as suggested reading on the users' dashboard. Content for the new Quit Guide feature supports users with setting and preparing for a quit date, learning about medications to assist with quitting, managing cravings and other withdrawal symptoms, handling high-risk situations, staying motivated, and recovering from lapses. The addition of the Quit Guide section matches Actify to the NCI QuitGuide app on the cessation content, allowing for stronger inferences about the specific effects of Actify's BAT-D components.

Comparison of Actify and QuitGuide.		
	Actify	QuitGuide
Treatment approach	Behavioral activation + USCPG	USCPG
Cessation content description	Static quit guide, push notifications with reminders to track activities and smoking	Static quit guide, push notifications with tips for quitting
Targeting (mood management)	In-depth, personalized based on user input into the in app tracking system; core function of app	Superficial, “manage my mood” feature
Interactive tracking/progress features	Mood, activities, smoking level	Mood, craving
Game elements for engagement	Badges (trophies) for progress	Badges (trophies) for progress

7.3 Concomitant Medication

Use of concomitant treatments for both tobacco cessation and depression will be assessed at each time point. Individuals who report using self-report any other quit smoking treatment, including FDA-approved quit smoking medications (e.g., nicotine patch, nicotine gum, Zyban), during the screening phase will not be eligible to participate in the study. At the 2 and 6-month follow-up assessment, participants will be asked about their use of FDA-approved quit-smoking and pharmacotherapy for depression. Initiating use of FDA-approved quit-smoking medications during the study is allowed.

7.4 2 and 6-Month Follow-up Data Collection

At baseline, we will collect email, phone, and mailing address information as well as optional contact information on up to two collateral contacts. At each follow-up, we will send reminder letters. The data collection protocol is as follows: Day -14: mail a \$2 pre-incentive letter (non-contingent incentives increase retention [86]) two weeks before the first online survey invitation; Day 0: First email invitation with link to online version of survey, with offer of \$10 bonus for completing the survey within 24 hours; Day 7: Second email invitation with link to online version of the survey; Days 10 to 18: Eight attempts to complete telephone version of survey (one call per day); Day 19: Send mailed version of the survey. Based on our WebQuit RCT trial experience (n=2,637), we estimate that this protocol will yield 89% data retention, and that 92% of respondents will complete the web-based version of the survey (68% within 24 hours and 32% after 24 hours).

7.5 Participant Compensation

Participants will receive up to \$124 for participating in this study. Specifically, at 2- and 6-month follow-ups, participants will receive compensation based on the following structure:

- \$2 in a pre-incentive letter for each follow-up (for a total of \$4)
- \$25 for each follow-up survey completed in any modality (for a total of up to \$50)
- \$10 bonus for completing the follow-survey within 24 hours of the initial email invitation (for a total of up to \$20)
- \$25 for completing saliva cotinine and smartphone application-based carbon monoxide testing, if asked, after the 2-month and the 6-month follow-up study survey (for a total of up to \$50)

Participants whose data are flagged for potential deception related to study eligibility criteria (e.g., age, US residence) will be contacted prior to compensation being provided in order to confirm eligibility. If eligibility cannot be confirmed, participants will not be compensated.

8.0 SUBJECT EVALUATION

8.1 Data Collection Overview

Table 1. Phase II Pilot Study Data Collection Overview

Measure	Screening	Baseline	8-week follow-up	6-month follow-up	Purpose
PHQ-8 (8 items)	X	X	X	X	Eligibility, mechanism of change
Other eligibility criteria (~11 items)	X				Eligibility
Demographics (~10 items)		X			Sample Description
FTND (6 items)		X			Sample Description
Treatment satisfaction (~8 items)			X		Acceptability
Treatment preferences (~5 items)		X			
Tobacco/Nicotine use (~12 items)		X	X	X	Efficacy
Behavioral Activation for Depression Scale (25 items)		X	X	X	Mechanism of change
Concomitant treatment (2 items)	X	X	X	X	Stratification, sensitivity analysis
Total number of items	36 items	70 items	53 items	45 items	
Estimated duration	~5-8 min	~10-15 min	~15-20min	~10-15 min	

8.2 Enrollment Procedures.

The study recruitment website provides basic information about the study, FAQ, information about the study team and Fred Hutchinson Cancer Research Center (FHCRC), and a portal to the informed consent form, screening, and baseline surveys.

We will use the identical enrollment method proven successful in our previous, remotely-conducted RCTs. Specifically, for participants who screen eligible on the recruitment website and provide their email address, we will instantly send them an email (and two reminders over a 14-day period) inviting them to complete a secured online survey to provide informed consent and complete the baseline assessment. Those not consenting and completing the online enrollment process within 14 days will be sent an email notifying them that they were not enrolled and provide both the QuitGuide app and the 800-QUIT-NOW phone number to reach their state's quitline.

To address potential fraudulent responses to web-based screening surveys, we will use the same methods used in our previous studies: CAPTCHA verification, ineligibility if the IP address was previously used or suspicious, and telephone contact by research staff if any aspect of automated data collection revealed suspicious activity (e.g., very brief survey completion times or unusual patterns in email addresses). To further deter fraudulent attempts to enter the study, no compensation will be provided for completion of the screening and baseline surveys.

Informed Consent. Participants will be asked to review and sign the online informed consent before completing the baseline assessment. The informed consent will encourage individuals to contact either [name] or the project manager ([name]) with questions about the study (contact information will be provided). The informed consent will be collected and stored in the secure database behind FHCRC firewall. Participants who complete the enrollment process will receive a copy of the informed consent via email for future reference.

Baseline Assessment. The baseline survey assesses demographics, smoking history and current smoking behaviors the use electronic cigarettes, mechanisms of change, and potential treatment moderators. More details below in section 7.3. The baseline survey data will be collected and stored in a research database behind FHCRC firewall.

After completing the baseline assessment, and first log-in, the participants will be randomized to receive either Actify or QuitGuide intervention. Randomization will be stratified based on sex assigned at birth, level of smoking and the presence of pre-treatment depressive symptoms.

Following the completion of the baseline and contact information survey the participant will receive a text message with a link to their phone. Once this link is clicked the study team will send an email and a text message indicating that they are enrolled in the study. This email and text message will provide them with a link to the randomly assigned intervention and login credentials. If in 3 days the participant has not opened the app, they will receive a text message reminder. If in 3 more days the participant has still not opened the app, study staff will reach out by phone and offer technical assistance.

8.3 Assessments/On-Study Clinical Evaluations

A complete schedule of assessments is provided in the table 1 above. All data from these assessments will be collected via web- based, telephone, or mailed surveys.

Eligibility and sample description. Demographic items assessed at baseline will include age, gender, sex assigned at birth, education, employment, income, and marital status. The 6-item Fagerström Test for Nicotine Dependence (FTND) [75] will be administered to assess degree of physical dependence on nicotine. Living with a smoker and quit attempts in the last 12 months will also be assessed. The Patient Health Questionnaire-8 (PHQ-8) is a widely-used assessment of depressive symptoms that has demonstrated ability to detect symptom changes over time as a result of treatment [91]. The scale scores range from 1 to 24, with severity thresholds as follows: 5-9=mild, 10-14=moderate, 15-19=moderately severe, 20-24=severe. A score of 10 has 88% sensitivity and 88% specificity for a diagnosis of major depression [6]. We elected to use the PHQ-8 rather than the PHQ-9 because (a) the suicidal ideation item on the PHQ-9, which is omitted from the PHQ-8, does not have a significant impact on the evaluation of depression severity, as the cut-off scores are the same for both versions, (b) because it would be impractical to conduct follow-up suicidality assessments and referrals for all screening completers who endorse any suicidal thoughts, and (c) because there is no reason to believe that behavioral interventions for tobacco cessation would increase the risk of suicidality and therefore require ongoing monitoring of suicidality as a safety assessment.

Treatment acceptability will be assessed at the 8-week end-of-treatment follow-up using measures of treatment utilization and satisfaction. *Treatment utilization* will include number of logins to the assigned application, determined objectively using custom web site analytics data. Consistent with our prior studies, *treatment satisfaction* will be assessed with 8 items on the 8-week outcome survey. Example

items include, “Overall, how satisfied are you with your assigned program?”; and “How useful was your assigned program?” Follow-up questions will probe satisfaction with specific components of the program (e.g. app content, app organization, push notification content, push notification frequency). These data are critical for making iterative improvements of the content and functionality of the app as it progresses through the development cycle.

Efficacy for smoking cessation will be self-reported 30-day point prevalence abstinence (PPA) at 8 weeks post-randomization (“Have you smoked at all, even a puff, in the last 30 days?”), consistent with our previous RCT of SmartQuit vs. QuitGuide for smoking cessation [10]. Secondary efficacy endpoints include: (1) 30-day PPA at 6-months post-randomization, (2) 7-day PPA at 8 weeks and 6 months, and (3) no use of cigarettes and other non-medicinal nicotine/tobacco products at 8 weeks and 6 months, including e-cigarettes. Use of these products will be measured at baseline and at 8-week and 6-month follow-up. Generally, biochemical verification of smoking abstinence is considered unnecessary in population-level interventions with no face-to-face contact [77]. However, we will confirm self-reported abstinence among those who report 30-day PPA at 8 weeks and at 6 months using saliva cotinine and expired carbon monoxide. Based on the just-published expert recommendations on biochemical confirmation of tobacco use and abstinence [90], our biochemical verification procedures will include both saliva cotinine testing as well as remote carbon monoxide (CO) monitoring using iCO Smokerlyzers. Both the cotinine tests and the Smokerlyzers will be sent to participants by mail. Participants will complete the CO testing on their smartphones using the iCO app and send results to the study team via email, using a function available within the app. We will also ask them to take a photo of the cotinine test results and return it via email. Aside from analysis of minor tobacco alkaloids (anabasine/anatabine, which require a urine sample and laboratory testing that would not be feasible in a remotely-conducted trial), this combination of methods is the best available approach that is feasible in a trial of this nature for differentiating distinct forms of nicotine and tobacco use. In order to meet the definition of biochemically-confirmed smoking abstinence, only the CO testing must be negative (<6 ppm for CO[1]). For analysis of abstinence from all forms of nicotine and tobacco, the CO test must be negative and the saliva cotinine must be negative for all abstainers who do not report recent (past 72 hours) use of nicotine replacement therapies. For those who report recent use of NRT, there is no feasible method of differentiating therapeutic use of nicotine from other forms of nicotine intake in this trial. We will report both self-reported abstinence and biochemically confirmed abstinence in all reports of study outcomes.

Mechanisms of change will be assessed using the PHQ-8 for depression and the 25-item Behavioral Activation for Depression Scale (BADS) [82], which was designed to assess activation as a treatment process targeted by BAT-D. Example items from the BADS scale include “I did something that was hard to do but it was worth it,” and “I made good decisions about what type of activities and/or situations I put myself in.”

Other assessments. Use of concomitant treatments for both tobacco cessation and depression will be assessed at each time point. Treatment preferences will be assessed with a single question and alcohol (AUDIT-C) will be assessed at baseline.

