Secondary Endpoints	
Treatment efficacy (e.g., smoking abstinence), changes in theory-based mechanisms of change.
 
Smoking abstinence outcomes:
 
 • Primary: Self-reported 30-day point prevalence abstinence (PPA) from smoking at 8 weeks post-randomization • Secondary: Self-reported 30-day PPA from smoking at 6 months post-randomization; Biochemically-confirmed 30-day PPA from smoking at 8 weeks and 6 months post-randomization; Self-reported and biochemically confirmed 7-day PPA from smoking at 8 weeks and 6 months post-randomization; Self-reported and biochemically confirmed 30-day PPA from cigarettes and other non-medicinal nicotine/tobacco products at 8 weeks and 6 months, including e-cigarettes

	
Mechanisms of change outcomes:
 
• Change in behavioral activation from baseline to 8 weeks post-randomization• Change in depressive symptoms from baseline to 8 weeks post-randomization
Type of control	Standard-care smoking cessation app (QuitGuide)
Treatment Groups	2 arm; Actify vs QuitGuide
Treatment Schedule	The treatment period is 8 weeks. Participants will be encouraged to use their assigned app as desired during that time.
Number of trial subjects	N=240
Estimated duration of trial	21 months
Duration of Participation	6 months

ABBREVIATIONS

BAT-D	Behavioral activation therapy for depression
PPA	Point Prevalence Abstinence
USCPG	US Clinical Practice Guidelines

Table of Contents

1.0	GENERAL INFORMATION	9
1.1	Protocol Title: An mHealth mood management tool to improve population-level cessation.....	9
1.2	Sponsor Information: National Institute on Drug Abuse, Grant Number: 1R34DA050967	9
1.3	Investigator Information: [name], [contact]	9
1.4	Contractors and Consultants for the Study (if applicable):.....	9
2.0	INTRODUCTION TO THE PROTOCOL	10
2.1	Introduction	10
2.2	Clinical Data to Date	13
2.2.3	Preliminary studies of mHealth apps for smoking cessation.	16
2.3	Risks/Benefits	16
3.0	PRE-TRIAL INTERVENTION USABILITY TESTING.....	17
3.1	Objectives:	17
3.2	Study Population:	17
3.3	Study Design:	17
3.4	Estimated Accrual:	18
3.5	Eligibility:.....	18
3.6	Registration.....	18
3.7	Usability Testing Overview	18
3.8	Participant Compensation	19
3.9	Enrollment Procedures	19
3.10	Assessments/Evaluations	20
3.11	Analytical methods	20
3.12	Objective.....	20
4.0	OVERVIEW OF CLINICAL TRIAL.....	21
4.1	Study Objectives	21
4.2	Study Population:	21
4.3	Study Design	21
4.4	Estimated Accrual:	22

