current use of another depression app, (3) severe depression (PHQ-9 ≥ 20) (3) current suicidal ideation (PHQ-9 item 9 score > 1), (4) receiving other treatment for smoking cessation, and (5) previous use of the SmokefreeTXT program.

[figure not shown]
Participants were recruited from the Seattle area primarily via no-cost Craigslist ads (59% of sample) and paid Facebook advertisements (41% of sample). We screened 72 individuals to enroll 17 participants in the single-arm trial, of whom 16 (94%) completed the in-person, 6-week follow-up visit and are included in the subsequent complete-case results. These participants were 56% men, 38% racial minority, and 25% Hispanic, with mean age of 36 (SD=10). There was strong engagement with the app: average number of logins per participant was 20 (SD=16). Average change in depression on the PHQ-9 was a 5-point decrease from baseline (SD=6), which was a statistically significant improvement in symptoms ($p=.009$). Average change in Behavioral Activation for Depression Scale (BADS) overall scale scores and activation subscale scores (Bat-D's theory-based change mechanism) were not statistically significant but were in the hypothesized direction: BADS total scores increased by 14 points, on average (SD=32; $p=.09$) and activation subscale scores increased by 4 points (SD=10; $p=.17$). The 7-day point prevalence abstinence rate at follow-up was 31% (5/16), and the 30-day PPA was 19% (3/16).

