7.2 Plans for final analysis

Data analyses will be conducted using the intent-to-treat approach, except where otherwise indicated. Analyses will consist of a comparison between two arms on three outcomes: acceptability, efficacy for smoking cessation, and effect on BAT-D theory-based mechanisms of change. The primary acceptability outcomes are number of app openings and overall satisfaction ratings. For smoking cessation, the primary endpoint is self-reported 30-day point prevalence abstinence (PPA) at 8 weeks post-randomization, which is comparable to the primary endpoints of the two extant trials of smartphone apps for smoking cessation [10, 34]. The secondary endpoints are self-reported and biochemically confirmed 7- and 30-day PPA at 6 months, 7-day PPA at 8 weeks, and biochemically-confirmed abstinence from any nicotine/tobacco product (other than FDA-approved cessation medications) between baseline and 8-week and 6-month follow-ups. For mechanism of change, the primary endpoint is the change in BADS scores between baseline and the 8-week follow-up and the secondary endpoint is the change in depressive symptoms over the same time period.

Linear regression will be used to evaluate treatment effects between the two arms for continuous endpoints (e.g. treatment satisfaction ratings). This model will adjust for any demographic or other variables that differ between study arms at baseline and are related to outcome as well as the stratification factors (depression severity, sex assigned at birth, and heaviness of smoking). To compare binary endpoints between two arms (e.g. smoking abstinence), a logistic regression model will be conducted with control for potential confounding variables and the stratification variable. Sensitivity analyses excluding participants using concomitant treatment for smoking cessation and/or depression will also be conducted.

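### Only reporters of 30-day abstinence are tested, so confirmed 7-day PPA duplicates confirmed 30-day PPA in the primary analysis; the confirmed all-nicotine endpoint also has two different windows

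*Combined protocol and SAP*

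**What the plan says.** **Who is tested.** The only testing rule is in the efficacy paragraph of 8.3: "we will confirm self-reported abstinence among those who report 30-day PPA at 8 weeks and at 6 months". Section 7.5 pays $25 for "completing saliva cotinine and smartphone application-based carbon monoxide testing, if asked, after the 2-month and the 6-month follow-up study survey", which names no wider group. The data collection table in 8.1 has no row for biochemical tests.

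**What confirmation requires.** Section 8.3 states: "In order to meet the definition of biochemically-confirmed smoking abstinence, only the CO testing must be negative". The threshold is below 6 ppm, and no separate criterion is given for the 7-day window.

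**Which endpoints carry the label.** The synopsis, 4.3.2 and DSMP 1.2 each list "Self-reported and biochemically confirmed 7-day PPA from smoking at 8 weeks and 6 months post-randomization". DSMP 7.2 says "The secondary endpoints are self-reported and biochemically confirmed 7- and 30-day PPA at 6 months", and then names 7-day PPA at 8 weeks without a clear label. Item (2) in 8.3 and the endpoint list in 14.2 give 7-day PPA with no mention of confirmation. However, the efficacy paragraph of 8.3 ends: "We will report both self-reported abstinence and biochemically confirmed abstinence in all reports of study outcomes".

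**Missing data.** Section 14.2 and DSMP 7.2 count missing smoking data as non-abstinent in the primary analysis, with complete-case and multiple-imputation results as sensitivity analyses. Neither has a rule for a test that was never requested.

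**All-nicotine/tobacco endpoint.** The synopsis, 4.3.2 and DSMP 1.2 list "Self-reported and biochemically confirmed 30-day PPA from cigarettes and other non-medicinal nicotine/tobacco products at 8 weeks and 6 months, including e-cigarettes". Section 14.2 and DSMP 7.2 instead describe confirmed abstinence over the interval from baseline to each follow-up, and name only the confirmed version. Item (3) in 8.3 gives no look-back window.

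**The concern.** A confirmed 7-day endpoint should show how many 7-day abstainers pass the test. Here the test is offered only to those who also report 30 days, so the 7-day result repeats the 30-day one. The gap between self-reported and confirmed 7-day PPA would partly consist of people who were never sent a kit, and a reader could take it for misreporting. Section 2.1.2.a presents biochemical verification as something this trial adds to earlier app studies, and 14.3 says the pilot estimates will help prepare the next trial.

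The second inconsistency is one of definition. An analyst working from 14.2 would derive a different all-nicotine variable from one working from the outcome lists.

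**Working it through.** **1. Does the testing rule make the two confirmed endpoints coincide?** Inputs: testing only if 30-day PPA is reported (8.3); confirmation needs a negative CO test (8.3); missing counts as non-abstinent (14.2, DSMP 7.2). Assumption: self-report is consistent, so 30-day abstinence implies 7-day abstinence.

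| Self-report | Tested? | CO result | Confirmed 7-day | Confirmed 30-day |
|---|---|---|---|---|
| Smoked in last 7 days | no | none | no | no |
| Abstinent 7 to 29 days | no | none | no | no |
| Abstinent 30 days or more | yes | negative | yes | yes |
| Abstinent 30 days or more | yes | positive | no | no |
| Abstinent 30 days or more | yes | not returned | no | no |

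The last two columns agree in every row. In the primary analysis the counts, rates and treatment effect are therefore the same at each time point.

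**2. Who falls in the gap?** For a survey on day D, 7-day PPA needs a last cigarette on or before D − 7, and 30-day PPA on or before D − 30. The untested band runs from D − 29 to D − 7, which is 23 days.
- 8 weeks, nominal D = 56: days 27 to 49.
- 6 months, D = 182 (assumed): days 153 to 175. For D = 180 the band is 151 to 173; for D = 183 it is 154 to 176.

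**3. Sensitivity analyses.** Among complete cases, an untested 7-day-only reporter is missing for confirmed 7-day PPA but a known non-abstainer for 30-day PPA. The numerators match; the denominators may not. Multiple imputation would have no tested 7-day-only participant to draw on.

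**4. Illustration.** In the single-arm Actify pilot (2.2.1.d), 7-day PPA was 5/16 (31%) and 30-day PPA 3/16 (19%).
- Under the 8.3 rule, (5 − 3)/5 = 40% of 7-day abstainers would have gone untested (exact 95% CI 5% to 85%).
- With missing counted as smoking, confirmed 7-day PPA could not exceed 3/16 = 19%.
- With complete cases, and if all three tests were returned negative, it would be 3/(16 − 2) = 3/14 = 21%.
- The other pair in the protocol, SmartQuit's depressed subgroup (2.2.1.d), is 23% and 6%: (23 − 6)/23 = 74% untested.

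**5. All-nicotine windows.** Thirty-day PPA is met if last use is on or before D − 30. Abstinence since baseline fails for any use from day 1. The definitions therefore disagree for last use on days 1 to D − 30.
- 8 weeks (D = 56): days 1 to 26. Last use on day 10, for example, meets one and fails the other.
- 6 months (D = 182, assumed): days 1 to 152. The upper end is 150 to 153 for D = 180 to 183.

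**6. Compensation ceiling.** 2 × $2 + 2 × $25 + 2 × $10 + 2 × $25 = $124, which reproduces 7.5. It already includes a test payment at both follow-ups.

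**The case against.** The strongest reply is that the main protocol's measurement and analysis sections never plan a confirmed 7-day endpoint: 8.3 item (2) and 14.2 leave the label off, and only the outcome lists and DSMP 7.2 add it. That is true, and it makes wording the likeliest source of the problem. It does not remove it, because the closing sentence of the 8.3 efficacy paragraph extends confirmed reporting to all outcomes.

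Also fair: phrasing the all-nicotine endpoint as an interval from baseline may be loose drafting. Entrants are current smokers interested in quitting within 30 days (5.1), so abstinence from the first day would exclude most who succeed later, and three lists already say 30-day PPA. That supports correcting the wording, but the sections still conflict as they stand.

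Four stronger readings are tempting and not supported:
- That 7-day abstinence would be hidden or understated overall. Self-reported 7-day PPA is its own endpoint and must be reported alongside.
- That the two confirmed endpoints are identical in every analysis. Complete-case denominators could differ, and the identity depends on consistent self-report and on untested counting as not confirmed.
- That the testing rule also distorts the 30-day all-nicotine endpoint. Anyone abstinent from all products for 30 days also qualifies for testing.
- That the pilot's 40% forecasts the gap here. That pilot had 16 completers, 6-week follow-up, only smokers with depressive symptoms, and SmokefreeTXT alongside the app.

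**Conclusion.** Both points hold in limited form. Under the stated testing rule, confirmed 7-day PPA carries no information beyond confirmed 30-day PPA in the primary analysis. This rests on consistent self-report and on applying the missing-equals-smoking rule to tests never requested. The 23-day untested band follows from the definitions; how many people fall in it cannot be predicted from the documents. The all-nicotine endpoint has two windows that, read literally, disagree at 8 weeks for last use on days 1 to 26, taking the survey at nominal day 56.

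The effect stops at secondary endpoints of a pilot that 14.3 says is not powered for group differences. The acceptability primaries, self-reported PPA and confirmed 30-day smoking PPA are untouched. This should be corrected, but it does not threaten the trial's main purpose.

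**What to change.** **Confirmed 7-day PPA: choose one.**
- *Wording only.* Remove the biochemical-confirmation label from 7-day PPA in the synopsis, 4.3.2, DSMP 1.2 and DSMP 7.2. Limit the last sentence of the 8.3 efficacy paragraph to the 30-day endpoints. No cost.
- *Widen testing.* In 8.3, test everyone who reports 7-day PPA (30-day abstainers are a subset) and keep the CO criterion. Label 7-day and 30-day smoking PPA as self-reported and biochemically confirmed, at both time points, in 8.3, 14.2 and DSMP 7.2. This costs one mailed kit and $25 per extra person tested. The $124 ceiling per participant is unchanged, though total spending rises. The number of extra tests is uncertain: 2 of 16 pilot completers (12.5%, exact 95% CI 1.6% to 38.3%) would have been added. If that share applied to 240 × 0.89 ≈ 214 respondents, it would mean about 27 extra tests per follow-up (range from the interval, 3 to 82), or 27 × $25 = $675 in payments plus kits. The protocol gives no kit price.

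**All-nicotine/tobacco endpoint.** In 14.2 and DSMP 7.2, restate it as 30-day PPA, both self-reported and biochemically confirmed, from any nicotine or tobacco product apart from FDA-approved cessation medications, at 8 weeks and 6 months. Add the 30-day window to item (3) in 8.3. This is wording only and adopts the window already in the three outcome lists.
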